7.2 Post Treatment Evaluation

Once the patient is no longer receiving treatment (as per section 3.9), he may receive follow-up calls to monitor his well-being and progress. For patients who are taken off treatment due to treatment toxicities, a follow up evaluation will be conducted within a month and if subject will be taken off study. The phone calls will likely be annual though no specific guidelines shall be set.

7.3 Off Study Criteria:

The patient will be considered off study upon either patient's death or patient's decision to no longer participate in the study or post treatment follow-up.

7.3.1 Off-Study Procedure:

Authorized staff must notify Central Registration Office (CRO) when a patient is taken off-study. An off-study form from the web site (<http://intranet.cancer.gov/CCR/welcome.htm>) main page must be completed and faxed to [contact].

8 Data Collection

8.1 Patient Records and Quality Assurance

Data will be collected according to GCP (Good Clinical Practice Guidelines). Complete medical records on each patient treated on the protocol, including primary documentation (e.g., laboratory reports, x-ray reports, scan reports, pathology reports, physician notes, etc.) will be maintained and confirm the following:

- The patient met each eligibility criterion.
- Signed informed consent was obtained prior to treatment. (An on-study confirmation of eligibility form will be filled out before entering the study.)
- Documentation of specific dates and times of all treatments, doses administered, and the reason for any dose modification.
- Toxicity was assessed according to protocol (see section 11).
- Response was assessed according to protocol (x-ray, scan, lab reports, dated notes on measurements, and clinical assessment, as appropriate).

Data will be entered in a secure electronic database, NCI C3D database. Completed eligibility checklists (developed by Central Registration Office, CRO), and blood sample flow sheets will also be stored. Copies of all expedited reports submitted to the IRB and IND Safety Reports will be kept in the regulatory binder. Complete records must be maintained on each patient, including the medical record with any supplementary information obtained from outside laboratories, radiology reports, or physician's records. These records will serve as the primary source material.

8.1.1 Drug Accountability

The unused satraplatin blister packs will be returned for drug accountability at each clinic visit. An oral study agent case report form will be used to document drug accountability for each patient on this study. Unused agent, which is not returned to the patient for the next dose cycle, will be disposed of according to the Procedure of Disposal of Returned Oral agents. The Investigator, or a responsible party designated by the investigator, must maintain a careful record of the inventory and disposition of all agents received from DCTD using the NCI Drug Accountability Record Form. See the CCR Standard Operating Procedure: *Conducting and Documenting Drug Accountability for Oral Investigational Agents that are Self Administered by Patients* (http://ccrintra.cancer.gov/clin_ops/policies/SOPCLIN1.pdf). Patients will use a diary to document daily drug intake and adverse events. (See Appendix B)

8.2 Evaluation of Disease

For the purposes of this study, patients should be re-evaluated for response every 2 cycles for the duration of the study.

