• CT (chest, abdomen, pelvis)
• Bone Scan
• Chest X-ray

Days 1-5 (Every Cycle)

Anti-emetic, oral administration
Satraplatin 80 mg/m² (rounded to the nearest 10), oral administration.

Days 1-35 (Every Cycle)

Prednisone 5 mg, twice daily, oral administration.
(Note* On days 1-5, prednisone will be taken 2 hours prior to Satraplatin dose.)

Every Cycle (+/- 4 days)

Follow-up evaluation
History and Physical Exam
Laboratory evaluation
PSA

Every 2 Cycles (+/- 4 days)

CT Scan (only if baseline CT shows positive disease)
Bone Scan

Every week:

Complete blood count with differential will be drawn (either at the Clinical Center or outside laboratory) for **Cycles 1-3**. If the Absolute Neutrophil Count (ANC) nadir is $\geq 1.5 \times 10^9/L$ and the platelet nadir is $\geq 100 \times 10^9/L$, CBC may be drawn only on Day 1 of each cycle starting with **Cycle 4**. If the ANC is $\leq 0.5 \times 10^9/L$ and the platelet count is $\leq 25.0 \times 10^9/L$, CBC with differential must be drawn at least 2 times per week or more, until resolved.

PRÈCIS

Background:

- Satraplatin is an oral, third-generation platinum analog that has recently been shown to increase PSA decline rates and progression-free survival in hormone-resistant prostate cancer.
- Satraplatin acts by binding to DNA forming intra- and interstrand cross links (DNA adducts), resulting in cell-cycle arrest in G2 phase and eventual apoptosis. One of the mechanisms that bring about resistance to platinum-based chemotherapy is removal of the platinum-DNA adducts by DNA repair pathways, called nucleotide excision repair (NER) and base excision repair (BER) pathways.
- Polymorphisms in the DNA repair genes causing impaired NER and BER capability has recently been shown in some cancers, including head and neck squamous cell carcinoma, non-small cell lung carcinoma, and ovarian carcinoma to predict better treatment outcome and response to platinum treatment.

Objectives:

- Primary objective of this single arm study is to determine if the presence of ERCC1 variant gene polymorphism which is involved with DNA damage repair may be associated with an impact on the progression-free survival of patients with metastatic prostate cancer.

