
1.2.5 Excision repair cross-complementation group 1 (ERCC1)

ERCC1 forms a heterodimer with XPF and as a unit, they perform the 5' incision which is specific to excision of Pt-DNA adducts.[49] Greater levels of total ERCC1 mRNA and full length ERCC1 mRNA were found in ovarian cancer tissues resistant to platinum-based chemotherapy.[42] The most widely studied polymorphism is 19007C>T (Asn118Asn), in which

the variant T allele was correlated to better response to platinum-based chemotherapy in epithelial ovarian cancer.[50] and oxaliplatin/5-FU combination chemotherapy in advanced colorectal cancer. [51] Another common SNP in ERCC1 is 8092C>A in 3' UTR. It was suggested that this variant may affect its mRNA stability which in turn results in reduced protein activity.[43] The variant A allele increased gastrointestinal toxicity in platinum treated NSCLC patients.[52] We have found that the ERCC1 N118N variant may occur at a lower frequency (around 20%) among African-Americans (unpublished data). It is unclear how this relates to the higher incidence of prostate cancer that is found in African-Americans. The frequency of the more widely studied polymorphism ERCC1N118N wild-type is also found to occur at around 20%, while variant alleles are about 80% (49% for the CT variant allele and 30% for the TT variant allele), in control groups of Caucasian men.. (unpublished data, please see Table on summary of key findings on variant DNA repair genes). Using these data, we propose that prostate cancer patients exhibiting ERCC1 variant alleles may have better response to a platinum agent such as satraplatin.

Table on summary of key findings on variant DNA repair genes in Caucasians and African-Americans (unpublished data)

Single Nucleotide Polymorphism	Genotype	Caucasian Counts (freq.)	African American Counts (freq.)	P VALUE
ERCC1N118N	CC	23(0.21)	96(0.76)	<0.001
	CT	53(0.49)	27(0.21)	
	TT	32(0.30)	4(0.03)	
	TOTAL	108	127	
ERCC1 C8092A	CC	77(0.53)	74(0.52)	N.S
	AC	59(0.40)	56(0.40)	
	AA	10(0.07)	11(0.08)	
	TOTAL	146	141	
ERCC2 K751Q	AA	49(0.42)	81(0.56)	<0.001
	AC	56(0.47)	57(0.40)	
	CC	13(0.11)	6(0.04)	
	TOTAL	118	144	
XRCC1 R399Q	GG			<0.001
	AG	49(0.46)	113(0.80)	
	AA	47(0.44)	26(0.19)	
	TOTAL	10(0.10)	2(0.01)	
		106	141	
XRCC1 R194W	CC	120(0.87)	133(0.90)	N.S
	CT	17(0.12)	14(0.09)	
	TT	1(0.01)	1(0.01)	
	TOTAL	138	148	

Single Nucleotide Polymorphism	Genotype	Caucasian	African American	P VALUE
		Counts (freq.)	Counts (freq.)	

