3.2.3 Hematologic toxicity Dose adjustments and reductions

Variable	Finding		Dose modification
	Platelets	ANC	

Variable	Finding		Dose modification
	Platelets	ANC	
Hematologic toxicity (based on previous cycle nadir*)	$\leq 25.0 \times 10^9/L$	$\leq 0.5 \times 10^9/L$	Decrease by $20\text{mg}/\text{m}^2$ dose
Delayed recovery for Retreatment due to hematologic toxicity**	Less than or equal to 6 weeks		No change in dose level
	Between 6 and 8 weeks		Decrease by $20\text{mg}/\text{m}^2$ dose
	More than 8 weeks		Off-study
Neutropenic fever			Decrease by $20\text{mg}/\text{m}^2$ dose***

*Complete blood counts must be available on a weekly basis in the previous course

**Time from Day 1 of prior cycle.

***Growth factor support may be given for subsequent cycles as clinically indicated

3.2.4 Retreatment guidelines:

If satraplatin dosing is interrupted during a treatment cycle, it may be restarted as long as the planned 5 days of dosing occurs within an 8-day period (maximum interruption=3 days).

If there is more than a 3 consecutive day delay, no further doses should be given in the cycle.

The patient will be allowed to begin the next cycle a minimum of 35 days after the first day of the previous cycle if the criteria for re-treatment are met.

Patients may be retreated every 35 days if the following criteria are met:

- Hematologic toxicity-Absolute neutrophil count is $\geq 1.5 \times 10^9/L$ and platelets $\geq 100 \times 10^9/L$
- Non-hematologic toxicity ascribed to study drugs must resolve to baseline or \leq grade 1, with the exception of alopecia; or \leq grade 2 for pain in order for re-treatment to continue.

Laboratory tests may be performed up to 48 hours prior to the scheduled study visit and if the retreatment criteria are met, the patient may be retreated. If the re-treatment criteria are not met, the patient may not be retreated until they are met. If therapy has to be held for more than 8 weeks from D1 of prior cycle, or > 3 weeks from the scheduled treatment, then the patient will be taken off-treatment.

With the approval of the Principal Investigator, patients may be evaluated in offices of other Associate Investigator's (listed in the protocol) every other cycle starting with pre cycle 4. Study medications will continue to be dispensed by the NIH pharmacy. Restaging scans will be performed at NIH

3.2.5 Dose Modification for Prednisone:

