5.3 IMAGING SUTIDES

Non-invasive imaging has become a standard tool in the clinic to monitor primary and metastatic solid tumors. CT scan and bone scan will be performed on all patients at study entry and after every 2 cycles to assess clinical response to satraplatin and prednisone. However, CT scan will only be obtained if baseline CT shows positive disease.

6 Concurrent Therapies

Concurrent hormonal therapy with GnRH agonists to achieve testosterone suppression will be allowed. Concurrent anticancer treatment with chemotherapy, radiation therapy, major surgical procedures for prostate cancer, and nonprotocol-related immunotherapy will not be permitted. No growth factor support will be given prophylactically prior to starting satraplatin.

Patients who require hematopoietic growth factor support (e.g. epogen, darbepoetin), NSAIDs and other maintenance medications prior to study entry will be allowed to continue their supportive therapies. Filgrastim and sargramostim or other bone marrow stimulants are permitted when clinically indicated only after the first cycle.

Premedication will be used with the initiation of therapy following Clinical Center Anti-emetic guidelines and administered 30 – 60 minutes prior to study therapy. If granisetron is used, additional anti-emetics must be taken 8 hours after granisetron dose. Other anti-emetics, take as prescribed.

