The trial will be conducted using a single stage design. However, to protect against the unlikely possibility that the agent will be associated with overall progression free survival which is substantially below what is expected based on results from other trials, an early stopping rule will be implemented as follows. After 20 patients have been enrolled and 6 months have passed since the 20th patient has enrolled, the proportion of patients who have attained 6 months without progression will be determined. If this fraction is no greater than 3/20 (15% who have attained 6 month progression free survival), then the trial will cease enrolling further patients because a one-sided 90% upper confidence bound on 3/20 is 30.4%, which would only indicate at best a modest probability of marginal consistency with what would be expected as the overall outcome using this agent. We will also perform genotyping for ERCC1 after the 20th patient, this is to test whether we are achieving the true probability of ERCC1 wild type proportion of 20% as indicated in earlier studies (in Caucasians). If the true probability is as shown, the probability of having 0 or 1 subject with WT genotype is tabled:

True WT proportion	Probability of getting 0 or 1 with WT
0.2	7%
0.1	39%
0.05	74%

Thus, if only 0 or 1 patient out of the first 20 patients should have ERCC1 WT genotype, then this would be more consistent with a 0.05 rather than a 0.20 true rate of WT. If this turns out to be the case, then we would re-evaluate the procedure for enrolling subjects to try to increase the proportion of patients with ERCC1 WT and amend the protocol accordingly.

Toxicity of the agent will also be tabulated for all patients taken as a group, and potentially by type of polymorphism genotype expression in the event that this may have some association. The distributions of toxicity identified will be compared informally to data from the same agent in other trials.

This trial will also explore other biologic correlates, as outlined above using genotyping for other DNA repair gene polymorphisms, white blood cell collections, and tumor biopsy, whenever possible. Monthly PSA, CBC, and serum chemistries will be performed at baseline and monthly thereafter, with CT scans and bone scans to be performed at baseline and every 10 weeks of treatment until progression. The comparisons will be made without any correction for multiple comparisons because of the exploratory and secondary nature of the evaluations.

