17 APPENDIX C. Study Calendar

Schedules shown in the Study Calendar below are provided as an example and should be modified as appropriate (+/- 1-2 days to allow for clinic variations around federal holidays).

Procedure	Screening/ Baseline	Every Cycle Days (1-5)	Every Cycle Days (1-35)	Every Cycle	Every 2 Cycles
Medical History	X			X	
Physical Exam	X			X	
Informed Consent	X				
Vital Signs	X			X	
Height	X			X	
Weight	X			X	
Performance Status	X			X	
Demographics	X				
Concurrent Medications	X			X	
Tumor Biopsy (optional)	X and C2D1				
Labs					
• CBC with diff					
• Platelet count					
• PT and apt					
• Chemistry Panel ^a					
• PSA					
• Testosterone level					
Correlative Research Studies ^b	X ^b				
Radiological Assessments					X
• CT Scan (chest, abdomen, pelvis)	X				
• Technetium ⁹⁹ Bone Scan					
Chest X-Ray	X				X
EKG	X				
Tumor Measurements	X				X
Adverse Events Evaluation	X			X	
SATRAPLATIN ^c		X			
PREDNISONE		X	X		

^a Chemistry Panel includes: electrolytes, BUN, creatinine, albumin, calcium, magnesium, phosphorus, alkaline phosphatase, ALT, AST, total bilirubin, total protein, LDH, testosterone level

^b If Correlative Research Study is missed prior to Day 1, may be drawn (one time blood draw) at any point throughout study.

^c Dose as assigned: route/schedule

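### Restaging is counted in cycles in four places and in weeks in section 9, so dose delays can move the scans and with them the genotype comparison of PFS

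*Protocol*

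**What the plan says.** Four places in the protocol count restaging in cycles:

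- the schema: "Every 2 Cycles (+/- 4 days", covering CT (if the baseline CT was positive) and bone scan;
- section 5.3: "CT scan and bone scan will be performed on all patients at study entry and after every 2 cycles";
- section 8.2: "patients should be re-evaluated for response every 2 cycles for the duration of the study";
- the Appendix C study calendar, whose imaging column is headed "Every 2 Cycles".

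Section 9 counts in weeks: "CT scans and bone scans to be performed at baseline and every 10 weeks of treatment until progression".

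Section 3.2.4 sets 35 days as the minimum time between cycle starts. The upper limit appears in the same section: "If therapy has to be held for more than 8 weeks from D1 of prior cycle", or more than 3 weeks past the scheduled date, the patient comes off treatment. No passage says whether a scan keeps its date when dosing is held.

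On genotype and toxicity, section 9 plans to tabulate toxicity by genotype in case there is an association. Section 1.2.5 cites one finding for the 8092C>A polymorphism: "The variant A allele increased gastrointestinal toxicity in platinum treated NSCLC patients".

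**The concern.** The primary comparison is the proportion progression-free at 6 months by ERCC1 genotype, with Kaplan-Meier and log-rank analyses of PFS as secondary. Radiographic progression is recorded when a scan shows it, so the scan dates are part of the endpoint. If they follow the cycles, they follow the reasons for delay, and those are mainly toxicity: section 3.2.4 makes retreatment conditional on neutrophil and platelet recovery and on resolution of drug-related toxicity.

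The trial's rationale is that variant carriers repair platinum damage less well, so a link between genotype and toxicity is conceivable. If one genotype group were delayed more often, its progression would on average be recorded later even with identical tumour behaviour, and the PFS curves would separate for a reason unrelated to efficacy. Apart from bias, a clinician following section 8.2 and one following section 9 could scan the same delayed patient on different dates.

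**Working it through.** **Interval.** Planned: 2 x 35 days = 70 days = 10 weeks, identical to section 9. Longest permitted: 2 x 8 = 16 weeks, reached only if both cycles run to the limit.

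**The plan's own figure.** Section 9 gives 80% power for a one-sided 0.10 Fisher's exact test, 20 wild-type against 46 other, 20% against 50% progression-free at 6 months. Exact enumeration over the two binomials gives 80.4%, so the stated figure is right and the same rejection region is used below.

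**Primary 6-month comparison, no true difference.** Assumptions (not from the protocol): exponential progression at the same rate in both groups, progression found only at scans, and 6-month status taken from the last scan by week 26. With section 9's overall 39%, S(t) = exp(-λt) and λ = -ln(0.39)/26 = 0.0362 per week. Wild-type patients are scanned at weeks 10 and 20, so their apparent 6-month PFS is S(20) = 48.5%. All variant patients are given the cycle length shown:

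| Variant cycle | Scans by week 26 | Apparent variant PFS | Type I error |
|---|---|---|---|
| 5 weeks | 10, 20 | 48.5% | 6.4% |
| 6 weeks | 12, 24 | 41.9% | 2.2% |
| 7 weeks | 14 | 60.2% | 25.7% |
| 8 weeks | 16 | 56.0% | 16.8% |

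The error falls when delay brings the second scan nearer to week 26 and rises when delay pushes that scan past it. With 8-week cycles in only half of variant patients it is 10.7%; in a quarter, 8.3%. If wild-type patients had the 8-week cycles instead, it is 1.8%, and power for a true 20% against 50% falls to about 54%, compared with about 77% when both groups are scanned every 10 weeks.

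**Random delays, no true difference.** Assumed: each cycle is independently delayed by 1 to 3 weeks, with probability 20% in wild-type patients and 20%, 40% or 60% in variant patients; 3,000 simulated trials per scenario. Pairs are Weibull (shape 0.62) / exponential progression times:

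| Delay, wild-type vs variant | Log-rank (permutation) | Fisher |
|---|---|---|
| 20% vs 20% | 10.2 / 10.9% | 6.7 / 6.8% |
| 20% vs 40% | 13.0 / 13.5% | 6.2 / 5.7% |
| 20% vs 60% | 15.8 / 15.3% | 7.3 / 8.8% |
| Calendar scans | 10.8 / 9.7% | 6.8 / 6.9% |

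The asymptotic log-rank test with exponential times runs slightly higher: 15.3% and 17.1% in the two unequal scenarios, against 11.1% on calendar scans.

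**How often the second scan passes week 26.** It is due at week 20 plus the delays of four cycles, so the total delay must exceed 6 weeks and at least three of the four cycles must be delayed. For delays uniform on 1 to 3 weeks, the total exceeds 6 with probability 1/2 given three delays and 23/24 given four:

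P = 4q³(1 - q)/2 + (23/24)q⁴

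- q = 0.2: 0.0128 + 0.0015 = 1.4%
- q = 0.4: 0.0768 + 0.0245 = 10%
- q = 0.6: 0.1728 + 0.1242 = 30%

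With delays in whole weeks the figures are 1%, 8% and 23%.

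**The case against.** **The passages scarcely conflict.** They are identical at the planned cycle length. Section 9 speaks of weeks of treatment, so it is not clearly a calendar clock either. This stands: section 9 cannot be taken as already containing the delay-proof rule. It leaves open what happens under delay, which is where the rules part.

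**Differential delay is not shown.** A reader might infer that progression is looked for later in one genotype group. The documents do not support that. They give no delay rates by genotype, and section 9 mentions a toxicity association only as a possibility. The one cited finding concerns 8092C>A, gastrointestinal toxicity and lung cancer, whereas the CC against CT/TT contrast used for the design is N118N. This stands, and the point is conditional for that reason.

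**The direction is not fixed.** A reader might also infer that any bias favours the one-sided hypothesis. For the primary endpoint it does not: 6-week variant cycles lower the type I error to 2.2%. In every random-delay scenario the Fisher test stays below its nominal 10%. The values of 16.8% and 25.7% need every variant patient on 8- or 7-week cycles.

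**The delay model is generous.** It keeps the delay probability constant, although sections 3.2.1 and 3.2.3 attach dose reductions to many such delays and section 7.1 ends therapy for limiting toxicity at the lowest level. Repeated long delays may therefore be rarer than assumed. Clinical progression found at the every-cycle visits would dilute the effect further. Both reduce its likely size. Neither removes the dependence of scan dates on toxicity.

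**Conclusion.** The point holds as a conditional one. As written, the protocol lets the time between restaging scans range from 10 to 16 weeks according to dosing delay, and its passages do not settle which clock applies. In a trial that compares PFS by genotype, this ties measurement of the endpoint to a post-baseline variable that may be related to the exposure.

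The clearest effect is on the secondary log-rank test: about 13 to 16% rejection under the null, against about 10 to 12% on calendar scans. This rests on assumed delay rates of 20% in wild-type and 40 to 60% in variant patients, none of which is in the protocol, and makes no allowance for dose reduction after delay or for progression found between scans. The primary Fisher comparison can move in either direction and on average moves little, so inflation of the primary test is not established. The change is worth making because it is cheap.

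**What to change.** Reconcile the passages to one assessment schedule counted in calendar weeks from cycle 1 day 1: every 10 weeks, +/- 4 days, until progression, regardless of dose delays. State it in the same words in the schema, sections 5.3, 8.2 and 9, and Appendix C. Section 9 needs the edit too, because its present wording does not say what happens when dosing is held. No dosing or treatment-stopping rule is touched.

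The cost is wording in five places and about the same number of scans. Some scan visits for delayed patients will no longer coincide with dosing visits.

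The change removes the dependence on delay but does not by itself place a scan at 6 months: week 26 still falls between the scans at weeks 20 and 30. Under the assumptions above, the apparent 6-month PFS would be 48.5% in both groups when the true value is 39%.
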